4 STUDY POPULATION

4.1 Selection of Study Population

The study will be conducted at Oslo University Hospital in Oslo, Norway. Only healthy volunteers will be included (see inclusion/exclusion criteria).

4.2 Number of Patients

12 volunteers will be recruited.

4.3 Inclusion Criteria

1. Healthy volunteers
2. Age 18 – 64
3. Both sex
4. No chronic disease
5. No regular medication
6. Recruited from the general population
7. Signed informed consent and expected cooperation of the subjects for the treatment and follow up must be obtained and documented according to ICH GCP, and national/local regulations

4.4 Exclusion Criteria

1. Use of pain medication the last 2 days before a session
2. Use of complementary medicine the last 2 days before a session
3. Use of regular medication
4. Previous substance abuse
5. Pregnancy
6. Know allergies or serious side effects to opioids or metoxyflurane
7. Use of alcohol last 24 h before each session
8. **Exclusion criteria with respect to fentanyl:**
9. Hypersensitivity opposite the active substance (fentanyl) or other opioids
10. Hypersensitivity opposite the excipients (to fentanyl): sodiumchlorid, water for injection, hydrochloric acid or sodium hydroxide
11. Respiratory depression without artificial ventilation

12. Use of MAO-inhibitor or use of MAO-inhibitor by two weeks before inclusion

13. Elevated intracranial pressure or brain trauma

14. Hypovolemia or hypotension

15. Myasthenia gravis

16. Exclusion criteria with respect to metoxyflurane:

17. Use metoxyflurane as anesthetic

18. Hypersensitivity opposite metoxyflurane or fluorinated anesthetics

19. Hypersensitivity opposite the excipient (to metoxyflurane): Butylhydroksytoluen

20. Malignant hyperthermia or persons with suspect genetic predisposition for malignant hyperthermia

21. History (to the volunteer or family) of serious adverse effects after administration of inhalation anesthetics

22. Volunteers showing sign of liver damage after use of metoxyflurane or halogenated anesthetics

23. History of liver disease

24. Clinical significant reduced kidney function or history of kidney disease

25. Changed of level of consciousness of any cause, including brain trauma, drugs or alcohol

26. Clinical detected cardiovascular instability

27. Clinical detected respiratory depression

5 TREATMENT

For this study Pentrox® (methoxyflurane) 3 ml / N02B G09 /Inhalation vapour, liquid, and the active comparator Fentanyl® / N01A H01 / Concentrate and solvent for solution for injection and intravenous use (with 2 different doses 0,025 mg and 0,05 mg) are defined as Investigational Medicinal Products (IMP). The dosages used for both methoxyflurane and fentanyl in this study are according to approved indications as described in the SPC for both drugs. NaCl 9 mg/ml (sodium chloride -saline) concentrate and solvent for solution for intravenous and inhalation use is also defined as IMP. NaCl 9 mg/ml will be used as placebo.

5.1 Drug Identity, Supply and Storage

Pentrox® (methoxyflurane), 3 ml / ATC-nr. N02B G09 / Inhalation vapour, liquid. For inhalation use. (Mundipharma).

Fentanyl® 2 ml, 0.05 mg/ml / ATC-nr. N01A H01 / Concentrate and solvent for solution for injection and intravenous use (Hameln).

Natriumklorid 9 mg/ml, 10 ml amp. / ATC-nr: B05BB01 / Concentrate and solvent for solution for injection and intravenous use (Braun). - placebo

Natriumklorid 9 mg/ml, 10 ml amp. / ATC-nr: B05BB01 / Concentrate and solvent for inhalation (Braun).- placebo.

All three drugs can be stored in room temperature. The drugs will be in a dark, locked storage room for medicines in Research nurse [name]'s office at the Department of Research and Development, Division of Emergencies and Critical Care, Oslo University Hospital. [name] will assist [name] in the study..

5.2 Dosage and Drug Administration

A nurse, not participating in the study, will prepare the drugs for use at each session.

- 1) Fentanyl 0.025 mg (0.5 ml) diluted with natriumklorid 9 mg/ml (1.5 ml), in a 2 ml syringe for intravenous use
- 2) Fentanyl 0.05 mg (1.0 ml) diluted with natriumklorid 9 mg/ml (1.0 ml), in a 2 ml syringe for intravenous use
- 3) Natriumklorid 9 mg/ml (2.0 ml) in a 2 ml syringe for intravenous use
- 4) Pentrox® Inhalator (methoxyflurane) 3 ml, Inhalation vapour
- 5) Pentrox® Inhalator (natriumklorid) 3 ml, Inhalation vapour

Timing of administration of drugs se 2.2 secondary endpoints, study's timeline.

The study medicines will be administered to the subject by authorized site personnel only ([name] and [name]).

5.3 Duration of Therapy

Every subject will receive 4 different treatments in a randomized sequence with an interval of at least 3 days between each session. Each session lasts for 2 hours. The actually time-line for the study is 30 min. The preparation before start will take 30 min. Then one hour of recovery before end of each session. Both drugs, methoxyflurane and fentanyl, will at that time be eliminated from the body.

5.4 Premedication and Monitoring

No premedication will be used.

Vital sign assessment (blood pressure and respiration frequency) will be registered during each session.

Continuous ECG, heart rate, ETCO2 and SpO2 measurement will be registered throughout each session.

5.5 Schedule Modifications

No dose modifications are allowed.

5.6 Concomitant Medication

No use of pain medication and complementary medicine the last 2 days before a session. No concomitant drugs are allowed to take.

Prohibited medication:

- Hypersensitivity opposite the active substance (fentanyl) or other opioids.
- Hypersensitivity opposite metoxyflurane, fluorinated anesthetics or butylhydroksytoluen
- MAO-inhibitor or use of MAO-inhibitor by two weeks before inclusion.

If any adverse effects we have rescue medications: naloxone (adverse effects to opioids), adrenalin (low blood pressure, anaphylaxis), atropine (low pulse) and ephedrine (low blood pressure and/or low pulse)

5.7 Subject Compliance

The study medicines will be administered to the subject by authorized site personnel only.

5.8 Drug Accountability

The responsible site personnel will confirm receipt of study drug and will use the study drug only within the framework of this clinical study and in accordance with this protocol. Receipt, distribution, return, and destruction (if any) of the study drug must be properly documented according to the sponsor's agreed and specified procedures.

The drugs will be stored according to Oslo University Hospital guidelines for narcotics before distribution (locked storage room for medicines). The drugs will be treated by a nurse not participating in the study. Any remaining study medicine will be logged in the CRF by the nurse before being disposed of according to hospital standards.

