9 DATA MANAGEMENT AND MONITORING

9.1 Case Report Forms

For Electronic Case Report Forms (eCRFs) and paper Case Report Forms (pCRF)

The CRF for this study will be designed and produced by research nurse [name] and principal investigator [name], Oslo University Hospital.

The designated investigator staff will enter the data required by the protocol into the paper Case Report Forms (pCRF/CRF). The Investigator is responsible for assuring that data entered into the CRF is complete, accurate, and that entry is performed in a timely manner. The signature of the investigator will attest the accuracy of the data on each CRF. If any assessments are omitted, the reason for such omissions will be noted on the pCRFs. Corrections, with the reason for the corrections will also be recorded.

The data will be entered into a database and double-checked for erroneous entries. The setup of the database system will be performed by research nurse [name], Oslo University Hospital, Ullevål. Oslo University Hospital has a safe database (K. sensitive) where the data will be saved.

After database lock, the investigator will receive a digital copy of the subject data for archiving at the investigational site.

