9.5 Database management

The data will be stored in a dedicated and secured area at:

- pCRF: in a locked filing cabinet in the office of research nurse [name] at the Department of Anesthesiology, Oslo University Hospital, building 7, Ullevål.

Data will be stored in a de-identified manner, where each study participant is recognizable by his/her unique trial subject number. The code list to link pCRF to patient in case of need for identifying data will be stored in a locked filing cabinet in the private office of research nurse [name] at the Department of Anesthesiology, Oslo University Hospital, building 7, Ullevål.

After transferal of data from pCRF to the database, the pCRF will be stored in the research archive at the Department of Anesthesiology, Oslo University Hospital, building 36, Ullevål.

- The database will be stored in the designated space in the secure research server for Oslo University Hospital (Domain "Felles"- "Sensitivt"; File "Forskning03").

The data will be stored until 31.12.2035.

Data management will be performed by research nurse [name] and principal investigator [name], Oslo University Hospital. The Data management procedures will be performed in accordance with the department's SOPs and ICH guidelines.

Data entered into the database will be validated by double-checking for erroneous entries against the CRF and hospital records.

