10.2.3 Blinding and emergency unblinding

The investigators ([name] and [name]) and the subject will be blinded for the randomization and the study medication. The subject may theoretically identify the study medication from drug characteristics, but we consider this unlikely.

A doctor and a nurse will pack and label the study medicine. They will not be blinded, but will not participate in the handling of the subjects.

Emergency unblinding should generally only be done if the safety and well-being of the subject is being compromised. The decision to reveal the treatment allocation during the study should be done exclusively by the principal investigator.

Un-blinding of the treatment allocation is permissible only if the safety and well-being of the subject is being compromised. The decision to reveal the treatment allocation during the study may only be done by the principal investigator. The date and time of un-blinding must be documented in the CRF and in the patient's hospital records.

In the event of an SAE, the Investigator will break the treatment code.

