10.4 Planned analyses

The main statistical analysis is planned when the planned number of patients have been included and have finalized data collection. Furthermore all data has to be entered, verified and validated according to the data management plan.

Prior to the main statistical analysis, the data base will be locked for further entering or altering of data. A separate statistical analysis plan (SAP) will provide further details on the planned statistical analyses. The SAP will be finalized, signed and dated prior to database lock. The treatment allocation will be revealed after the database lock and used in the statistical analysis. There will be no interim analysis.

Deviation from the original statistical plan will be described and justified in the Clinical Study Report. Amendments to plan can be done until day of DB lock.

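### Section 5.8 puts the unblinded nurse's record of leftover study drug in the CRF that blinded investigators complete and sign; unless coded or restricted, that entry can reveal treatment before database lock

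*Combined protocol and SAP*

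**What the plan says.** **Who handles and logs the drug.** Section 5.8: "The drugs will be treated by a nurse not participating in the study". It continues: "Any remaining study medicine will be logged in the CRF by the nurse before being disposed of according to hospital standards". Section 5.2 also has a nurse from outside the study prepare each session's drugs. Section 10.2.3 says that the doctor and nurse who pack and label are unblinded and take no part in handling the subjects.

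**Who works with the CRF.** Under Section 9.1 designated investigator staff fill in the paper CRF, and "The signature of the investigator will attest the accuracy of the data on each CRF". Section 9.5: "Data management will be performed by research nurse", together with the principal investigator.

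**What the blind requires.** Section 10.2.3 says that the investigators and the subject "will be blinded for the randomization and the study medication". Section 10.4: "The treatment allocation will be revealed after the database lock and used in the statistical analysis".

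**What is left open.** Section 5.8 does not say whether the entry gives drug names, volumes or only a code, or who may see it. It refers receipt, return and destruction to sponsor procedures that are not reproduced. No section describes a separate accountability log.

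**The concern.** Section 5.2 makes every syringe 2 ml and puts 3 ml in the inhaler whether active or placebo, so that what reaches the bedside does not show the treatment. What stays behind after preparation is not matched in this way. An open record of it in the CRF would give blinded staff the information that the matching is meant to hide.

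Two things are at stake:

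- **Later sessions.** The outcome is a subjective 0-10 pain rating, in sessions run by the investigators. Each volunteer receives all four treatments, so identifying one session narrows those that remain. An investigator who knows this may instruct the volunteer differently, or judge differently whether a mild opioid effect needs recording (Section 8.1.1).
- **Decisions before lock.** The criteria for major protocol violations are settled before lock, and the primary analysis uses only subjects without them (Section 10.3). The analysis plan may be amended until the day of lock (Section 10.4). These decisions should be taken without knowledge of treatment. Withdrawn subjects are not replaced (Section 6.4.1), so excluding one of 12 volunteers removes 1/12 = 8.3% of the sample.

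**Working it through.** **Inputs.** Section 5.1: fentanyl comes as 2 ml at 0.05 mg/ml, and saline in 10 ml ampoules, listed separately for intravenous and inhalation use. Section 5.2: syringe and inhaler contents. Section 5: saline is itself defined as an investigational product, so leftover saline also falls under Section 5.8. Abbreviations follow the plan's flow chart: C control, F1 fentanyl 0.025 mg, F2 fentanyl 0.05 mg, M methoxyflurane.

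**The plan's own volumes.** Volume drawn = dose / concentration.

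- F1: 0.025 / 0.05 = 0.5 ml, which matches "Fentanyl 0.025 mg (0.5 ml) diluted with natriumklorid 9 mg/ml (1.5 ml), in a 2 ml syringe for intravenous use".
- F2: 0.05 / 0.05 = 1.0 ml, also as stated.
- Syringe totals: F1 0.5 + 1.5 = 2.0 ml; F2 1.0 + 1.0 = 2.0 ml; C and M 2.0 ml of saline. The syringes match.

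**Leftovers at preparation.** Leftover = ampoule volume - volume drawn. Assumption: a fresh ampoule is opened for each use.

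| Treatment | Fentanyl left | Saline left, i.v. ampoule | Saline left, inhalation ampoule | Saline left if one ampoule serves both uses |
|---|---|---|---|---|
| C | none opened | 10 - 2.0 = 8.0 ml | 10 - 3 = 7 ml | 10 - 2.0 - 3 = 5.0 ml |
| F1 | 2.0 - 0.5 = 1.5 ml | 10 - 1.5 = 8.5 ml | 7 ml | 10 - 1.5 - 3 = 5.5 ml |
| F2 | 2.0 - 1.0 = 1.0 ml | 10 - 1.0 = 9.0 ml | 7 ml | 10 - 1.0 - 3 = 6.0 ml |
| M | none opened | 8.0 ml | none opened | 10 - 2.0 = 8.0 ml |

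**What each form of entry would disclose.**

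- Fentanyl by volume only: F1 and F2 are identified; C and M are not told apart. Per volunteer, two of four sessions are identified, so 12 x 2 = 24 of 12 x 4 = 48, and the other 24 are known to be C or M.
- Fentanyl and all saline by volume: all four treatments are identified, whether the saline comes from one ampoule or two.
- Residue in the coded 2 ml syringe only, or an envelope code: nothing need be disclosed.

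**Reach within a volunteer.** An entry made after a session cannot alter that session's score. Entries can bear only on sessions 2 to 4, at most 12 x 3 = 36 of 48 (leaving aside any inference across volunteers from the block design, which is kept in a separate document). If every entry were decodable and read, the chance of guessing the next treatment would rise from 1/4 to 1/3, then 1/2, then 1.

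The sample size, power and significance level do not enter this check and do not change.

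**The case against.** The strongest reply is that Section 5.8 does not say what is written down. The entry could be the residue in coded units, which are matched by volume and issued in identical opaque envelopes (Section 5.9). The sponsor procedures it cites could set a safe format. The plan also uses CRF broadly, since Section 8.5.1 counts the investigator site file as part of it, so the entry need not lie among the session pages. That the nurses of Sections 5.2, 5.8 and 10.2.3 are one person is a reasonable reading, but it is not stated.

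Much of this stands, and it limits the point to a missing safeguard. It does not remove it. Dose changes are barred (Section 5.5), so a syringe given as planned leaves nothing to log, and the natural subject of the sentence is the ampoule remainder. Procedures that the reader cannot see cannot be assumed to override an explicit instruction to use the CRF.

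Three stronger readings are tempting but not supported:

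- **Every session is revealed.** A reader might infer that all 48 treatments become known. That requires entries by drug and volume, including saline, that investigators actually read. The plan states neither the content nor the access.
- **Section 5.8 contradicts the blinding sections.** It does not. An entry confined to codes would satisfy Sections 5.8, 10.2.3 and 10.4 together.
- **The store is also a leak.** Section 5.1 says: "The drugs will be in a dark, locked storage room for medicines in Research nurse", and goes on to name that nurse's office. A reader might infer that a stock count shows what was used. No section describes such a count by that nurse, the store is locked, and with names removed it cannot be established whether that nurse is one of the blinded investigators.

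**Conclusion.** The concern holds as a gap in the protection of the blind. Information from unblinded staff is sent to a record that blinded staff complete, sign and help manage, with no stated restriction. If leftovers are logged by drug and volume, fentanyl alone identifies F1 and F2, and fentanyl with saline identifies all four treatments. The consequence is possible unblinding of investigators for a volunteer's later sessions, and for judgements before lock on protocol violations and plan amendments. The volunteer gives the rating and is not described as seeing the CRF, so the volunteer's own blinding is untouched, as is the score of a session already completed.

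This rests on three assumptions: the logging nurse is the unblinded preparer, a fresh ampoule is opened per use, and the principal investigator is among the blinded investigators. The size of any bias cannot be calculated from the documents. The point should be fixed before the first session, because a lost blind cannot be restored afterwards. It does not show that the double-blind claim is false.

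**What to change.** In Section 5.8, change where leftovers are recorded. Suggested text: *Leftover study medicine is recorded in a separate drug-accountability log, held by the unblinded, non-participating staff away from investigators and data managers until database lock. The CRF carries at most the envelope code.* The envelopes are already numbered (Section 10.2.2), so no new identifier is needed. If the sponsor's procedures already provide such a log, Section 5.8 should say so and drop the reference to the CRF.

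The cost is one extra paper form. No staff are added, because the same nurse already makes the entry. The downside is that the monitor, who already covers supply accountability under Section 9.3, must check this log separately and raise queries on it only with the unblinded staff. Section 5.1 needs no change on this account.

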5.9 Drug Labeling

The investigational product will have a label permanently affixed to the outside and will be labeled according with ICH GCP and national regulations, stating that the material is for clinical trial / investigational use only and should be kept out of reach of children.

Labeling of the IMPs will be done by one a nurse anesthetist not participating in the study. The study drugs, will be distributed in a pre-packed in identical, opaque envelopes (the same day as the drugs will be used). The envelopes are not to be broken until randomization of the patient is done

The labeling will be in Norwegian. One label is attached to the syringe with the most critical information: organizer serial number; "Til klinisk utprøving"; Oppbevares utilgjengelig for barn; See pictures:

Labels will also include blank lines (in Norwegian) for:

- Patient's initials
- Patient's enrolment code
- Protocol code
- Date dispensed
- Name of prescribing doctor
- Name of Principal Investigator

5.10 Subject Numbering

Each subject is identified in the study by a unique subject number that is assigned when subject signs the Informed Consent Form. Once assigned the subject number cannot be reused for any other subject. A record in the clinical study file will keep track of the next number to assign. Once assigned the subject number cannot be reused for any other subject.

6 STUDY PROCEDURES

6.1 Flow Chart

Screening period within 1-14 days of treatment. Inclusion/exclusion evaluation. A medical history will be performed.

Three pilots will be performed before the study start to investigate whether the two selected doses are representative to compare with the 3 ml metoxyflurane dose. If the pilots demonstrate large differences in the CPT scores at time zero between the selected fentanyl doses and metoxyflurane, a change in the protocol has to be performed. This will lead to an application to REK about the changes (and the Norwegian Medicines Agency).

Flow chart:

Time (min)	-15	-10	-5	0	5	10	15
Control (C)	CPT		placebo (NaCl) i.v. placebo (NaCl) inhal; continuous	CPT			CPT
Fentanyl (F1)	CPT		F1 0.025 mg i.v. placebo (NaCl) inhal; continuous	CPT			CPT
Fentanyl (F2)	CPT		F2 0.05 mg i.v. placebo (NaCl) inhal; continuous	CPT			CPT
Metoxyflurane (M)	CPT		placebo (NaCl) i.v. M 3 ml inhal; continuous	CPT			CPT

Abbreviations: NaCl: natriumchloride, i.v: intravenously, inhal: inhalation, CPT: Cold pressor test.

Each session starts with a CPT (time -15 minutes). Then a 10 minutes rest before the subject receives a syringe of either NaCl or a dose of fentanyl intravenously (time -5 min). At the same time the subject begin to inhale either metoxyflurane or NaCl through the inhalator. The subject should first take 10 breath through the inhalator. This will take approximately 1-1.5 minutes. The subject then take a break, and then inhale the rest of the dosage before time zero.

At time zero a new CPT will be performed. At time 15 min the last CPT will be performed.

The subjects will undergo CPT (cold pressor test) to determine the analgesic effect of the drugs.(13,14) The CPT will be conducted using a temperature-controlled bath with circulating 3°C water (FP 45-HE Refrigerated/Heating Circulator,

Julabo Labortechnik, 77960 Seelback, Germany). The subjects submerge their right hand to the wrist with fingers abducted for up to 90 s. The endpoints are NRS scores every 10 s. This test will be performed 3 times for each session.

The actual implementation of the study will take 30 minutes. We estimate 30 minutes of preparation and 1 hour of observation after the execution of the protocol. Totally, each session will last for 2 hours.

A cannula will be placed on the subject left hand back. The right hand will be submerged into the ice water.

Pulsoxymetry, ETCO₂ and ECG will be continuously monitored during the study. Necessary acute medical equipment is available (Lærdalsbag, suction, intravenous liquid, naloxone. In addition anesthetic drugs: adrenalin, atropine and ephedrine).

Side effects will be recorded: sedation, dizziness, itching, nausea and vomiting. Respiration frequency and non-invasive blood pressure will be recorded every 5. min

